3.1 Study Population

This study will recruit adolescents between ages 14-17, inclusive, who are able to read and speak English, who have a negative or unknown HIV status; and who have engaged in high-risk sexual activity (see **Table 1**) in the last 12 months. The study will also recruit adults who are able to read and speak English, who are a parent or guardian to an adolescent who is between ages 14-17, inclusive, and who have a negative or unknown HIV status. Adolescent and parent participants will be recruited from four U.S. cities: Baltimore, MD; Chicago, IL; Denver, CO; and Tampa, FL. These cities have diverse populations, high rates of incident HIV infection among adolescents and young adults, and/or demonstrated success in recruiting minor adolescents for biomedical HIV research. Recruitment will be primarily clinic-based, but if that method proves insufficient for recruiting participants, we will employ a variety of strategies for recruitment including: social media advertising, fliers, and word of mouth.

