3.2 Sample Size

This study will enroll approximately 144 (36 per study site) high-risk minor adolescents and 144 (36 per study site) parents of adolescents. A subset of 24-32 (6-8 per study site) adolescents and 24-32 (6-8 per study site) parents will be selected to participate in the debriefing interview. Of note, the adolescents and parents will not be parent-child dyads; they will be unrelated. We project total enrollment of 288 participants, however, since this is a multi-site project with simultaneous recruitment with a hard to reach population, we may schedule and enroll more subjects than anticipated.

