3.3 Study Randomization, Stratification, or Description of Non-Random Assignment Procedures

Adolescents will be randomized in a 1:1:1 ratio into 1 of the 3 consent conditions using block randomization with block size k=3 (so that in every 3 subjects, exactly 1 is allocated to each condition). The randomization will be stratified by study site and sex assigned at birth. Within study site, sex assigned at birth, and consent condition, the order in which the hypothetical trials will be presented to adolescents will be block randomized with block size k=2.

Enrollment of parents will be restricted to approximately 15 parents of adolescent natal males and 15 parents of natal adolescent females at each study site. Parents will indicate the acceptability of each of the three consent conditions for each of the two hypothetical trials. Independently of the gender strata, the order of hypothetical trial presentation will be block randomized with blocks size k=2. Separately for each hypothetical trial, the order of evaluation for the three consent conditions will be randomized so that each ordering is equally likely.

A subset of 6-8 adolescents (3-4 natal males and 3-4 natal females) and 6-8 parents of adolescents (3-4 parents of natal males and 3-4 parents of natal females) at each site will be selected for participation in the debriefing interview. All study participants will be asked if they are willing to participate in the debriefing interview until quotas have been reached.

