4.2.1 Able to read and speak English; and

4.2.2 Parent or guardian of an adolescent who is between ages 14-17; and

4.2.3 not the parent of a child already enrolled in the study.

Table 1. Criteria for high-risk sexual behavior

High-risk sexual behavior criteria for natal males	High-risk sexual behavior criteria for natal females
During the last 12 months, which of the following is true for you? (check all that apply): 
• I had unprotected anal sex with a male• I had protected anal sex with 3 or more males• I had sex with a male for money, gifts, shelter, or drugs	During the last 12 months, which of the following is true for you? (check all that apply): 
• I had unprotected anal or vaginal sex with a male• I had sex with someone who is HIV+• I had protected vaginal or anal sex with 3 or more males

• I had sex with a male, and I have had a sexually transmitted infection (gonorrhea, chlamydia, syphilis, herpes)• I had sex with someone who is HIV+• I had anal sex with a male and the condom slipped off or broke• None of the above	
• I had sex with a male for money, gifts, shelter, or drugs• I have had sex with one or more males, and I have had a sexually transmitted infection (gonorrhea, chlamydia, syphilis, herpes)• I had vaginal or anal sex with a male and the condom slipped off or broke• None of the above
---	---

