5.2 Randomization Procedures

5.2.1. Adolescent Participants

Adolescents will be randomized in a 1:1:1 ratio into 1 of the 3 consent conditions using block randomization with block size k=3 (so that in every 3 subjects, exactly 1 is allocated to each condition). The randomization will be stratified by study site and sex assigned at birth. Within study site, sex assigned at birth, and consent condition, the order in which the hypothetical trials will be presented to adolescents will be block randomized with block size k=2.

A subset of 6-8 adolescents (3-4 of both sexes) at each site will be selected using quota sampling for participation in the debriefing interview. Participants will be asked if they are willing to participate in the debriefing interview unless the quota for their demographic group has been reached.

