10.3 Sample Size and Power Estimates

This study is powered to detect a meaningful difference in adolescent WTP scores and to detect a meaningful difference in parental WTS scores between the three consent conditions being studied. The WTP scores will be estimated as the mean score of three 5-point Likert scales. Based on the assumption that adolescent WTP scores are normally distributed and analyses using a linear regression model based on 120 participants (40 per consent condition) and with 7 independent variables in the model will provide 80% power to detect a $0.09 f^2$ effect size, which is between a small ($f^2=0.02$) and a medium effect size ($f^2=0.15$), for consent conditions. This power calculation, which assumed a single observation per participant, is conservative and the actual study which will have two observations per participant (one for each simulated consent process) will have a larger statistical power to detect an $f^2=0.09$ effect size for consent condition. Since the test of consent condition effects based on parental WTS scores is a within-participant comparison rather than an across-participant comparison, a test of parental consent condition effects will have 80% power to detect an even smaller effect size (f^2) compared to tests for consent condition effects using adolescent WTP scores.

A subset of 24–32 (6–8 per study site) adolescents and 24–32 (6–8 per study site) parent participants will be selected to participate in the debriefing interview. Prior research with similar populations suggest that this sample size is sufficient for eliciting a variety of perspectives and establishing key themes in the data.

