10.4 Statistical Analysis Plan

10.4.1 Quantitative Data Analysis

The primary analyses will estimate the effect of the three conditions and two hypothetical trial types on adolescent WTP scores and parent WTS scores. All analyses will be performed separately for adolescents and parents. The type I error rate will be set to $\alpha = 0.05$ separately for adolescent-specific and parent-specific hypothesis tests.

Linear mixed models will be used to estimate the effect of the three consent conditions and two trial types on WTP and WTS scores, with a random participant effect (i.e. random intercept) to account for the potential correlation between the multiple responses per participant. Aside from consent condition and trial type effects, the LMMs will also include adolescent's sex assigned at birth and study site as fixed effects.

Heterogeneity of consent condition and trial type effects across study sites will be evaluated. If statistically significant interactions occur ($p<0.05$), site-specific estimates of effects will be presented to supplement the pre-planned analyses. P-values from pairwise comparisons of consent condition effects will be adjusted for multiple comparisons to control the type I error rate at the level $\alpha=0.05$ separately for parents and adolescents. Tests of trial type effects will be performed at the level $\alpha=0.05$ separately for adolescents and parents and separately from tests of consent condition effects.

As a secondary sensitivity analysis, we will evaluate whether concern about HIV, family context (frequency of communication, connectedness), and other demographic and socioeconomic factors affect WTP/WTS participation in biomedical research. We will examine these effects by adding variables into the models to determine if they moderate the relationship between consent condition and WTP/WTS scores.

Although WTS and WTP scores are discrete, it is common to analyze these data using linear models. Research suggests that this approach is robust to the discrete nature of the data if the normality assumption is not severely violated. However, usage of the LMM may be problematic if a large number of responses occur on the boundary (e.g. a high proportion of 1's or 5's). In this case we will fit a linear quantile mixed model for the median WTP and WTS scores, which does not require normality.³⁴

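### Adolescents are randomised within eight site-by-sex strata but the adolescent models adjust for site and sex only additively; if the sex gap differs between sites, the consent-condition standard errors will be slightly conservative.

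*Combined protocol and SAP*

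**What the plan says.** Section 3.3 sets the allocation: "Adolescents will be randomized in a 1:1:1 ratio into 1 of the 3 consent conditions", "using block randomization with block size k=3". Section 5.2.1 repeats the scheme and names the strata: "The randomization will be stratified by study site and sex assigned at birth". Section 3.1 gives the number of sites: "Adolescent and parent participants will be recruited from four U.S. cities". Four sites and two sexes make eight separately blocked cells. On enrolment, section 3.2 states: "This study will enroll approximately 144 (36 per study site) high-risk minor adolescents". No male-female split is given for adolescents.

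Section 10.4.1 specifies linear mixed models with consent condition, trial type and a random participant intercept, and adds that "the LMMs will also include adolescent's sex assigned at birth and study site as fixed effects". The same sentence is used for the adolescent UBACC model. The interactions to be examined are those of consent condition and of trial type with site. A site-by-sex term is not among them. Section 10.3 bases power on a "linear regression model based on 120 participants (40 per consent condition) and with 7 independent variables". That count fits an additive model: 2 for condition, 1 for trial type, 1 for sex and 3 for site (my inference; the seven are not listed).

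**The concern.** Blocks of three equalise the consent conditions inside every site-by-sex cell, apart from incomplete last blocks. Any difference in mean score between cells therefore cannot move the consent contrast. An additive model removes the part of those differences due to site and to sex, but not the part due to their interaction (3 degrees of freedom). That part is left in the between-participant variance, mainly in the random-intercept term.

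Each adolescent sees only one consent condition, so the Aim 1 comparison is between participants and its standard error is built from that variance. If the sex gap varies by site, the reported standard errors exceed the true ones, the test runs below its nominal 5%, and some of the precision gained by stratifying is not used. The adolescent trial-type contrast is within participants and is unaffected. So are the parents' consent and trial-type contrasts, because each parent rates every condition for both trials and cell differences cancel.

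A varying sex gap is conceivable. Table 1 sets separate entry criteria by sex ("High-risk sexual behavior criteria for natal males" in one column, a different list for natal females in the other), and section 4.3.1 allows extra recruitment sources when recruitment is slow, which could be used unevenly across sites.

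**Working it through.** **The plan's own figure.** Inputs from section 10.3: N = 120, 7 predictors, f² = 0.09, 80% power; α = 0.05 from section 10.4.1. The consent test has 2 numerator df and 120 − 7 − 1 = 112 denominator df. With Cohen's noncentrality, 0.09 × (2 + 112 + 1) = 10.35, power is about 82%, and the f² giving exactly 80% is 0.086, which rounds to 0.09. The stated figure reproduces. (With noncentrality f² × N, power is 83.5%.)

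**Set-up.** Let r be the share of the variance of participant mean scores, after site and sex main effects, that site-by-sex explains. The documents give no value, so r is an assumption and a range is shown. With two scores per adolescent, the consent contrast is equivalent to a comparison of participant means.

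- Standard error, additive relative to eight-stratum model: 1/√(1 − r).
- Type I error of the additive model at N = 144: denominator df 144 − 7 = 137 (intercept, 2 condition, 1 sex, 3 site), critical F(2,137) = 3.06. The true error rate is P[F(2,137) > 3.06/(1 − r)].
- Power after adding the 3 terms: replace f² by f²/(1 − r) and use 10 predictors, with noncentrality f² × N. The 80% base at N = 120 uses f² = 0.0825.

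| r | SE too wide by | Type I error, additive | Power from 80% base, N = 120 | Power at f² = 0.09, N = 144 (additive 90.05%) |
|---|---|---|---|---|
| 0 | 0 | 5.0% | 80.0% | 90.04% |
| 1% | 0.5% | 4.9% | 80.4% | 90.3% |
| 5% | 2.6% | 4.3% | 82.1% | 91.5% |
| 10% | 5.4% | 3.6% | 84.2% | 92.9% |

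For r = 5%, for example, 1/√0.95 = 1.026 and 3.06/0.95 = 3.22.

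**Simulation check.** 144 adolescents, 18 per cell (assumed), blocks of 3, 4,000 runs per setting, least squares on participant means:

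- r = 0: additive SE 0.2035 against a true 0.203–0.205; type I error 5.4% under both models.
- r = 5%: additive SE 0.204 against a true 0.197–0.200; type I error 4.6% additive, 5.3% with eight strata; power 85.1% against 86.3%.
- r = 10%: additive SE 0.204–0.205 against a true 0.193–0.195; type I error 3.4% against 4.8%; power 86.2% against 89.1%.

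The spread of the condition estimates was the same under both models. Only the reported standard error changes.

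**What r = 5% means on the 1–5 scale.** Assume SD 1.1 and within-person correlation 0.6. The variance of a participant mean is 1.21 × (1 + 0.6)/2 = 0.968. Suppose the sex gaps at the four sites deviate from their average by +0.6, +0.2, −0.2 and −0.6. The cell deviations are half of these, with mean square (0.09 + 0.01 + 0.01 + 0.09)/4 = 0.05, and 0.05/0.968 = 5.2%. So r of about 5% needs a 1.2-point spread in the gap. By the same scaling, 1% needs about 1.2 × √(0.00968/0.05) = 0.5 point and 10% about 1.2 × √(0.0968/0.05) = 1.7 points.

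**The case against.** The strongest reply is that nothing in the documents shows a site-by-sex interaction. Table 1 is the same at every site, so different criteria for the sexes predict a sex main effect. Different recruitment sources by site would predict a site main effect. Both are already in the model. This stands: the interaction is possible, not shown.

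The larger values of r also need large differences. Under the SD and correlation assumed above, the planned effect (f² = 0.09, three equally spaced conditions) spans 2 × √(1.5 × 0.09 × 0.968) = 0.72 point between the extreme conditions. The 5% case needs a nuisance spread of 1.2 points, which is larger. This too stands and points to the lower end of the range.

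The equal sex split is assumed; the 18/18 split in section 5.2.2 is for parents. With 27/9 per site the same gaps carry 4 × 0.75 × 0.25 = 0.75 of the variance, so 5.2% becomes 3.9%. That lowers the size but does not remove the mechanism, and the eight-stratum model also held about 5% type I error with uneven splits.

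A reader might infer that the planned standard errors are too wide as a matter of fact, or that the stratification is ignored. The documents support neither. With no interaction the additive standard errors are correct, and both stratification factors are in the model. Nor does the plan break a commitment: type I error stays at or below 5%, and the additive model matches the power calculation's predictor count.

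**Conclusion.** The adolescent models leave out 3 df of the randomisation structure. The consequence is conditional and small: if the sex gap in mean score varies by site, the consent-condition standard errors are conservative, by 0.5% to 5.4% for r between 1% and 10%. The gain from modelling the strata is about 0.4, 2 or 4 power points from an 80% base at r = 1%, 5% or 10%, or about 0.3, 1.5 or 3 points at N = 144 and f² = 0.09. Condition estimates are unbiased under either model, and the stated 80% power is met either way.

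These sizes rest on an assumed r and on near-complete balance within cells; the simulation also assumes 18 adolescents per cell. This is an optional efficiency refinement, not an error that undermines the primary analysis.

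**What to change.** In section 10.4.1, for the adolescent WTP model and the adolescent UBACC model, replace the separate site and sex effects with the eight-level randomisation stratum (site by sex, 3 more df). Leave the parent models as they are: parents are not randomised to a consent condition within these cells, and their contrasts are within participant. Make the change before outcome data are seen.

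The cost is one line of wording and 3 of 137 between-participant df at N = 144. If there is no interaction, the loss is under 0.1 power point at N = 120 or 144. No new data are needed.

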3.0 STUDY DESIGN

This study will use a quasi-experimental design to explore how the informed consent process affects the acceptability of biomedical HIV prevention trials, from the perspective of behaviorally high-risk minor adolescents and the parents of minor adolescents. All study participants will complete a computer assisted self-interview (CASI) that collects demographic, social, behavioral, and attitudinal measures. Adolescent participants will undergo a simulated consent process for each of two hypothetical studies based on their randomized consent condition (Appendix II). Parent Participants will undergo a simulated consent process that mimics what their own adolescent would hear while consenting for each of the two hypothetical studies. After each hypothetical study, parent participants will complete a CASI with three vignettes that describe each of the three possible consent conditions. Parents will rate the acceptability of each vignette. The order of vignettes, and the order of the two hypothetical studies, is varied to reduce the possibility of ordering bias. Hypothetical Study 1, modeled after ATN 113, is an open-label study of oral TDF-FTC and hypothetical Study 2, modeled after HPTN 077, is a Phase IIa trial of an injectable HIV integrase inhibitor.

Eligible adolescent participants will complete a demographic questionnaire, then be lead by RS through a simulated study consent process for one of two hypothetical studies. The consent process will be consistent with their randomly assigned consent condition. After completing the simulated consent process, the adolescent will complete a CASI assessing adolescents' WTP and will work with RS to complete the UCSD Brief Assessment of Capacity to Consent (UBACC)²⁵. The

simulated consent process and follow-up assessments will then be completed for the second hypothetical study. After the second UBACC, the adolescent will complete overall WTP, medical mistrust, and end of study questions.

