Eligible parent participants will first complete a demographic questionnaire. They will then review the informed consent form for the first study with the RS and complete a CASI assessing the acceptability of three approaches to consent, presented in three different vignettes (please see section 3.4.2 for further information). Parents will work with RS to complete the UCSD Brief Assessment of Capacity to Consent (UBACC)²⁵. The simulated consent process and follow-up assessments will then be completed for the second hypothetical study. After the second UBACC, the participant will answer a series of questions via CASI.

A subset of adolescent and parent participants will be selected to participate in a debriefing interview.

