5.3 Investigation Procedures

RS will prepare the participant's iPad for the beginning of the study visit. Adolescents will complete demographic, social, and attitudinal measures by CASI. Once completed, RS will begin

the simulated consent process for study 1 or study 2 (depending on randomization) by reviewing the hypothetical consent form (which reflects the randomly assigned consent condition; Appendix II). RS will allow time for questions about the hypothetical study from the participant, provide answers as needed. The RS will then ask the adolescent to complete the WTP questions on their iPad. Finally, the RS will administer the UCSD Brief Assessment of Capacity to Consent (UBACC)²⁵ for study 1 or study 2 (depending on randomization). The RS will then repeat the simulated consent process, WTP, and UBACC for the additional hypothetical study (study 1 or study 2 depending on randomization).

For parent participants, RS will prepare the participant's iPad for the beginning of the study visit. RS will begin the simulated consent process for study 1 or study 2 (depending on randomization) by reviewing the hypothetical consent form (which reflects the randomly assigned consent condition; Appendix II). RS will allow time for questions about the hypothetical study from the participant, provide answers as needed. The RS will then ask the parent to read the vignettes and answer WTS questions on their iPad. Finally, the RS will administer the UCSD Brief Assessment of Capacity to Consent (UBACC)²⁵ for study 1 or study 2 (depending on randomization). The RS will then repeat the simulated consent process, vignettes and answer WTS questions, and UBACC for the last hypothetical study (study 1 or study 2 depending on randomization). Parents will then complete demographic, social, and attitudinal measures by CASI.

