6.2 Enrollment/Entry

RS will prepare the participant to complete demographic, social, and attitudinal measures by CASI. Adolescent participants will complete these measures in two parts. The beginning CASI will include demographic information, SES, parental monitoring, and concern about HIV and the final CASI will include overall WTP, medical mistrust, and closing questions. Parent participants

will complete demographics, SES, WTS, concern about HIV, medical mistrust, and closing questions during the final CASI. The measures are summarized in **Table 2**, below.

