The primary endpoint analyses will be based on the observed data. By study design requirement, it will not be possible for sex assigned at birth to be missing and so no methods for missing covariates are needed for the primary analyses. If a key demographic or socioeconomic measures are missing in more than 5% of participants, the secondary sensitivity analyses described above will utilize multiple imputation by chained equations for those analyses.³⁵

The effect of the three conditions on the mean adolescent UBACC scores will be estimated using linear mixed-effect models (LMMs) that include a random participant effect (i.e. random intercept) to account for correlation between the multiple UBACC assessments per participant. Aside from consent condition and trial type effects, the LMMs will also include adolescent's sex assigned at birth and study site as fixed effects.

The effect of the trial type on the mean parent UBACC scores will be estimated using LMMs that include a random participant effect (i.e. random intercept) to account for correlation between the multiple UBACC assessments per participant. Aside from trial type effects, the LMMs will also include adolescent's sex assigned at birth and study site as fixed effects.

Using the same strategy described in Section 6.1 (e.g., to evaluate how demographic factors affect WTP/WTS participation), we will perform analyses that evaluate the extent to which capacity to consent, as measured by the UBACC, influences WTP/WTS scores.

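### In adolescents, UBACC is recorded after the randomised consent process and after WTP, and is analysed as an outcome of consent condition, so it cannot also serve as a moderator or cause of WTP

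*Combined protocol and SAP*

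**What the plan says.** **Allocation.** Section 5.2.1: "Adolescents will be randomized in a 1:1:1 ratio into 1 of the 3 consent conditions".

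**Order of measurement.** For each hypothetical trial the adolescent goes through the consent process for the assigned condition, then answers WTP, then takes the UBACC. Section 5.3 has: "The RS will then ask the adolescent to complete the WTP questions on their iPad. Finally, the RS will administer the UCSD Brief Assessment". Section 3.0 gives the same order: "After completing the simulated consent process, the adolescent will complete a CASI assessing adolescents' WTP and will work with RS" to complete the UBACC. The abstract, Section 10.1 and Appendix I agree.

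**UBACC as an outcome.** Section 10.4.1: "The effect of the three conditions on the mean adolescent UBACC scores will be estimated using linear mixed-effect models", with consent condition, trial type, sex assigned at birth and site as fixed effects.

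**UBACC as an explanatory variable.** The last paragraph of 10.4.1 says the analyses will "evaluate the extent to which capacity to consent, as measured by the UBACC, influences WTP/WTS scores". It reuses the strategy for demographic factors. The cross-reference is to Section 6.1, which is the screening section; the strategy meant appears to be the secondary analysis in 10.4.1 itself, where variables are added to the consent-condition model to test whether they moderate the effect of condition. Section 2.0 also lists capacity to consent among the Aim 1 moderators.

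**What is absent.** No measure of capacity taken before randomisation is described. Nothing is said about handling a covariate that is measured after randomisation.

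**The concern.** A moderator should be fixed before the exposure whose effect it modifies, and a cause should precede its effect. For a given trial, adolescent UBACC is shown to do neither. The plan also regards an effect of consent condition on UBACC as possible, because it sets out to estimate one. UBACC covers voluntariness (Section 3.4.3), which could plausibly depend on whose permission is required.

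Two things follow. First, if condition changes UBACC, adolescents with the same UBACC score in different conditions are no longer the groups that randomisation made comparable, so a consent contrast adjusted for or stratified by UBACC loses the protection of randomisation. Second, an association between WTP and a score taken afterwards cannot show that capacity drives willingness. Capacity is a stated sub-aim, so the result is likely to be reported, and a reader could take from it that capacity alters how the consent model works.

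**Working it through.** **1. The plan's own figure, used here only as a yardstick.** Section 10.3 states 80% power at f² = 0.09 with 120 adolescents and 7 predictors. With 2 numerator df, 120 - 7 - 1 = 112 denominator df and noncentrality 0.09 × (2 + 112 + 1) = 10.35, power is 81.9%. Exactly 80% needs f² = 0.086, which rounds to 0.09, so the figure reproduces. For three equal groups with evenly spaced means, f² = d²/6, so the design effect between extreme conditions is d = √(6 × 0.09) = 0.73 SD.

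**2. Inputs for the bias.** The documents give none. Assumed, in within-condition SD units:
- a = difference in UBACC between extreme conditions, 0.3 to 0.5
- r = correlation of one unmeasured trait with UBACC and with WTP, 0.5 to 0.7
- no true effect of condition on WTP

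**3. Formula.** In a linear model, the UBACC-adjusted contrast = total contrast - a × g, where g is the within-condition slope of WTP on UBACC. If the shared trait is their only link, g = r × r.

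| a | r | bias = -a × r² | rejection rate, condition adjusted for UBACC | rejection rate, condition-by-UBACC interaction |
|---|---|---|---|---|
| 0.3 | 0.5 | -0.3 × 0.25 = -0.075 SD | 5.5 to 6.4% | 4.8% |
| 0.5 | 0.5 | -0.5 × 0.25 = -0.125 SD | 8.1 to 8.7% | 5.1% |
| 0.5 | 0.7 | -0.5 × 0.49 = -0.245 SD | 20.5 to 21.5% | 4.9% |

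The rejection rates are at a nominal 5%, from simulations with 144/3 = 48 per condition and one observation per adolescent; ranges are across repeat simulations. With a = 0 and r = 0.5 the bias is 0 and the rejection rate 5.0%. The model without UBACC stays at about 5%. The largest bias shown is 0.245/0.73, about a third of the design effect.

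**4. With a true effect.** At a = 0.5 and g = 0.3, a true contrast of 0.50 SD becomes 0.50 - 0.15 = 0.35 SD.

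**5. WTP feeding into the later UBACC.** Suppose condition acts on UBACC only through WTP, with slope s. Then a = s × c for a true contrast c, g = s, and the adjusted contrast is c × (1 - s²). For c = 0.50 this is 0.455 at s = 0.3 and 0.375 at s = 0.5. If c = 0, this route gives no bias.

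**6. When there is no bias.** The shift is zero if neither condition nor WTP affects UBACC, or if UBACC is unrelated to WTP within condition.

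**The case against.** The strongest reply is that no primary result is touched. The primary mixed model contains condition, trial type, sex assigned at birth and site, and no UBACC. The UBACC work is secondary, and the plan nowhere says that a UBACC-adjusted contrast will replace the primary one. That stands. A reader who infers that the trial's main consent comparison is biased would go beyond the documents.

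The planned question is moderation, and under the assumptions above the interaction test keeps its 5% level. That also stands: the rates of 5.5 to 21.5% belong to the adjusted main effect and must not be quoted as the error of the moderation test. A correct rejection rate under one mechanism does not, however, make an interaction with a post-randomisation score evidence that capacity modifies the consent effect.

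UBACC measures understanding of what was disclosed, so it can only follow disclosure, and that understanding may have formed before WTP was answered. This is fair: late recording does not prove that the construct came second. It does leave the direction unidentified. First-trial UBACC precedes second-trial WTP, but it is still post-randomisation, and the plan does not say which score is used.

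It is also tempting to extend the point to parents, because Section 6.2 says they "will complete demographics, SES, WTS, concern about HIV, medical mistrust, and closing questions during the final CASI". The documents do not support that for the consent contrast. Every parent rates all three conditions, so a parent-level score such as concern about HIV, entered additively, is constant across conditions and cannot shift the contrast. Parent UBACC, taken once per trial after all three ratings, is likewise constant across conditions within a trial. Section 3.0 ("Eligible parent participants will first complete a demographic questionnaire") does not place concern about HIV first, and moving those items ahead of the vignettes would risk priming the parents' primary endpoint.

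**Conclusion.** The point holds for adolescents and for the secondary analysis of UBACC and WTP. As written, the plan would support a causal or moderation statement about capacity that a score taken after randomisation, and after the outcome for the same trial, cannot bear.

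The consent contrast in that model *can* be biased; the documents do not show that it *will* be. The range of about -0.07 to -0.25 SD rests entirely on the assumed UBACC shift and trait correlations, and on a linear model with one observation per adolescent rather than the planned mixed model with two. This is an inexpensive correction worth making before analysis. It is not a threat to the primary result.

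**What to change.** In Section 10.4.1:

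- State that adolescent consent-condition effects are reported only from models without UBACC.
- Report the UBACC-WTP relation as an association within consent condition, and replace *influences* with *is associated with*.
- State that a condition-by-UBACC interaction will not be interpreted as effect moderation by capacity, because UBACC is measured after randomisation. Align the Aim 1 sub-aim in Section 2.0 with this.
- Correct the cross-reference to Section 6.1 in the same edit.

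The cost is wording only: no added participants, visits or instruments, and no change to the order of CASI screens. The downside is a weaker answer to the capacity sub-aim, which becomes descriptive.
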